4.5. Study procedure

The study to be conducted will be single-blinded, randomized controlled, parallel design. The study population will consist of Seventy-two (72) male and female subjects conforming to the following admission criteria. The subjects meeting the admission criteria with an anticipation of 40% dropout rate will be stratified into two groups balanced for MGI, BOP, PI, and gender using screening data. In this single-blind design, product assignment will be randomized after screening, and only the PI and the Study coordinator will have access to the randomization key.

One group will be assigned to a new power toothbrush while the control group will be assigned an ADA approved manual toothbrush. The study involves a 12-week home use of the respective toothbrushes. Both groups will refrain from the regular use of mouthwash and any interdental device, such as floss, floss picks, toothpicks, water flossing device or interdental brush, during the length of the study. Written instructions on brushing and professional brushing demonstration will be provided at the outset of the study and each participant from both test and control groups will also receive a 2-minute timer to help them monitor their brushing time. Before each visit, subjects are expected to have at least 7 hours, but no more than 12 hours of accumulated, non-brushed, undisturbed plaque/debris.

The study includes four or five visits – screening, baseline, 2-week follow-up, 4-week follow-up and 12-week follow-up. Schematic 1 summarizes the study procedure and visits and Table 2 details procedures in this study. The Screening and the baseline visit may happen on the same day.

Schematic 1. Study and visit procedures

CONFIDENTIAL

CONFIDENTIAL

Visit 2: Baseline
(continued)

A

Use brush per instruction

PI examination after
brushing

Single use
result

Schedule next visit

Pre visit

7 – 12 hours of plaque
accumulation

Visit 3: Follow-up visit
at 2 weeks

Oral examination for tissue abrasion and MGI
by calibrated examiners

Periodontal probing for BOP and PPD
by calibrated examiners

Oral examination for PI
By calibrated examiners

Schedule next visit

Pre visit

7 – 12 hours of plaque
accumulation

Visit 4: Follow-up visit
at 4 weeks

[figure not shown]
Oral examination for tissue abrasion and MGI
by calibrated examiners

Periodontal probing for BOP and PPD
by calibrated examiners

Oral examination for PI
by calibrated examiner

Schedule next visit

A

CONFIDENTIAL

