Table 2. Procedure overview during visits

Procedure	Performed by	Visit				
		Screening	Baseline	2-week	4-week	12-week
Plaque accumulation	Subject	X	X	X	X	X
Patient information						
Informed consent form	Study coordinator/staff	X				
Patient demographics	Study coordinator/staff	X				
Medical/dental history	Study coordinator/staff	X				
Oral examination	Blinded examiners					
Oral cavity abrasion exam	Examiners 1 and 2	X	X	X	X	X
Gingival Index (MGI)	Examiners 1 and 2	X	X	X	X	X
Probing Pocket Depth	Examiners 1 and 2	X	X	X	X	X
Bleeding Index	Examiners 1 and 2	X	X	X	X	X
Plaque Index	Examiners 3 and 4	X	X*	X	X	X
Examiner calibration	All examiners	X				X
Others						
Inclusion/exclusion criteria	Study coordinator/staff	X	X			
Prophylaxis	Dental hygienist					X
Randomization	Unblinded staff/study coordinator		X			
Product introduction and instruction	Unblinded staff/study coordinator		X			
Brushing at clinic	Subject		X			
Scheduling future visit	Study coordinator/staff	X	X	X	X	
Collect used brushes	Unblinded staff/study coordinator					X
Exit survey	Subject					X

*Twice

CONFIDENTIAL

Visit 1: Screening and enrollment

Subjects will be asked to report to the clinic with at least 7 but no more than 12 hours of accumulated, non-brushed, undisturbed plaque/debris. Prior to screening, subjects will sign a consent form after having gone over the consent with a member of the study staff and having all questions answered. In this visit, subjects will be asked about dental and medical history related to the admission and exclusion criteria.

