At the screening exam, subjects will receive an oral soft tissue exam with periodontal probing, modified Gingival Index on the Ramfjord teeth, and the amount of stain and calculus will be noted. Following these examinations, the subject's plaque will be disclosed with Trace 28 solution (4 drops under tongue) and they will swish for 10 seconds. Next, subjects will rinse with 10 ml. of tap water twice for 10 seconds each. Disclosed plaque will then be recorded on buccal and lingual surfaces of the Ramfjord teeth using the Lobene modification of the Turesky Plaque Index. If baseline happens on the same day then full mouth GI and BOP will be carried out prior to disclosing for full mouth plaque measurements. Subjects who meet the admission criteria will be allowed to enroll. If a subject fails the screening exam due to oral disease such as, but not limited to dental caries and periodontitis, the subject will be appropriately referred to the main Marquette University School of Dentistry (MUSoD) screening clinic to insure that they will be given an opportunity for full diagnosis and treatment at the school of dentistry or some other appropriate clinic.

Each clinical index will be scored by one of two or three calibrated examiners. The oral cavity/oral safety exam and all measures of inflammation, the MGI, PPD and BOP will be carried out by examiners #1 and 2 while disclosing and scoring of the PI will be scored by examiners #3 and 4. A fifth examiner who is dual calibrated will be used if needed. Each examiner will be calibrated to the indices used, and will demonstrate repeatability of measures initially at the screening/calibration phase as well as during the study.

Visit 2: Baseline

Subjects who have signed consent form and met all the inclusion criteria and none of the exclusion criteria will be entered into the baseline procedure (day 0). This visit may occur the same day as screening.

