In this visit, subjects will first be evaluated for signs of soft or hard tissue trauma, and then full mouth Modified Gingival Index followed by full mouth probing of pocket depth and assessment of BOP. Teeth with calculus will be recorded. After these data are recorded each subject will be disclosed and full mouth Plaque scores assessed and recorded by a calibrated examiner. Any scorable teeth that have plaque buildup on any six tooth sites will be recorded. The subjects will then leave the examining area to the randomization and toothbrush distribution area where they will be provided their assigned brush out of site of the examiners. Group A will be given a power toothbrush, while Group B will be given a manual toothbrush. Both groups will also be given a two minute timer and the same fluoride toothpaste (Colgate Cavity Protection toothpaste) as well as the appropriate set of written instructions on tooth brushing. The subjects in the test group will follow the instructions provided by the manufacturer, while subjects in the control group will be given a standard written and both groups provided visual instructions on proper brushing. A study staff member will be available to answer any questions pertaining to the instructions and coach patients toward optimal brushing technique. Then the subjects will be required to use the brush assigned for two minutes before being sent back to the examiner to

CONFIDENTIAL

have a post-brushing plaque index recorded. These pre- and post 2-minute brushing data will be collected to assess single use effect differences between the toothbrush types. Subjects will be reappointed and instructed to bring their assigned brush to the subsequent exam sessions in a brown bag to avoid unmasking any of the examiners.

Visit 3: Two-week follow-up

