The first follow-up will take place two weeks after the baseline visit. Subjects can schedule the visit for any time between two days before and after the two-week use period (12-16 day range). Clinical examinations will be given to the subjects in the same order as the baseline visit with the exception that no second plaque index will be recorded. All subjects must present with 7 to 12 hours of undisturbed plaque. The oral safety exam will include a thorough examination of the gingiva to look for any signs of gingival trauma, irritation or abrasion. Any subjects who show signs of gingival trauma that appears to be toothbrush related will be exited from the study. The recorded findings will be reported as Adverse Events. In addition, any site in the mouth that shows an increase in probing pocket depth of 2 mm or greater from the baseline measurement will have that particular site treated with subgingival scaling and root planing or whatever the PI deems appropriate therapy. If subjects meet any of the discontinuation criteria, they will be withdrawn from the study.

Visit 4: Four-week follow-up

This visit should take place four weeks after the baseline visit within three days before and after the four week mark (25-31 day range). Subjects will receive full mouth examinations in the same order as the previous visit. Additionally, inspection for signs of gingival trauma and increase in PPD greater than 2 mm from the baseline will be conducted and evaluated. The PI will determine if any subject meets the discontinuation criteria as well as appropriate therapy to treat.

Visit 5: 12-week follow-up

In this visit, subjects will return the products, including manual toothbrush, or brush head, brush handle, and charger. The procedure is similar to the four-week follow-up visit, in which full mouth clinical examination will be carried out as before on each of the subjects. The subjects' disclosed plaque will be evaluated as usual. The examined results will be recorded. Prophylaxis will be carried out as needed.

The used brushes/brush heads will be returned to sponsor at the end of the trial and examined for wear as an additional measure of compliance.

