5.2. Exclusion Criteria

Any subject meeting one of the following criteria will not be included in the study.

1. Daily user of interdental cleaning devices, such as floss, floss picks, toothpicks, interdental brush, water flossing device
2. Regular user of antimicrobial mouthrinses within one week of entry into study
3. Professional prophylaxis within one month of entry into the study
4. Use of antibiotics within one month prior to the baseline exam
5. Signs of moderate to severe periodontitis or caries, categorized as PPD of 5 mm or higher and attachment loss of 3 mm or higher
6. Subjects with orthodontic bands and/or dental appliances.
7. Participated in an oral care related study in the last 90 days prior to this study
8. Pregnant or lactating women
9. Patients with a history of significant cardiovascular disease, diabetes, cancer, AIDS, or other organ impairment that would preclude their participation in the study
10. Acute/concurrent illness such as hepatitis, herpes simplex infections, influenza, etc.
11. History of rheumatic fever, cardiovascular valvular disease, artificial joint replacement or kidney or liver disorders
12. Chronic use of NSAID's (≥ 325 mg/day)
13. Current Smoker (within the last 3 months)
14. Other medical or dental conditions that would affect the study
15. Inability to commit to all necessary study visits from baseline to 12 weeks

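### Blinded examiners may see a subject's earlier scores, which could dull change-from-baseline scores in both arms; a minor second point is that a holder of the randomization key may also re-check eligibility at baseline

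*Combined protocol and SAP*

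**What the plan says.** **Access to earlier scores.** Section 8 first says that source access should be limited during the study, then gives blinded examiners access until its end. The patient schedule has the subject take the record to each station at baseline and at 2, 4 and 12 weeks. The list of items in the patient record names, for each visit up to week 4, one item covering oral cavity exam, gingival index, bleeding and pocket-depth charting, and another for plaque. The baseline plaque item covers both the pre- and post-brushing scores. Section 10 keeps all of a patient's forms in one booklet.

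Section 4.5 (Visit 3) requires treatment of "any site in the mouth that shows an increase in probing pocket depth of 2 mm or greater from the baseline measurement". It does not say who makes that comparison. Table 2 has Examiners 1 and 2 measure pocket depth, and the same pair score MGI and bleeding. Section 4.3 makes the 12-week change from baseline in bleeding and MGI the primary endpoint.

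**Allocation.** Section 4.5 randomizes after screening and states that "only the PI and the Study coordinator will have access to the randomization key" (here PI means the principal investigator). It adds: "The Screening and the baseline visit may happen on the same day". In Table 2 the row "Inclusion/exclusion criteria" belongs to the study coordinator or staff and is marked at screening and at baseline. Randomization at baseline belongs to "Unblinded staff/study coordinator". Under Visit 2, only subjects who have "met all the inclusion criteria and none of the exclusion criteria will be entered into the baseline procedure". After baseline scoring: "The subjects will then leave the examining area to the randomization and toothbrush distribution area".

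**The concern.** A change-from-baseline endpoint needs the follow-up score to be made without reference to the baseline score. MGI is a visual 0–4 judgement at each site. An examiner who can see the previous sheet may settle on or near the earlier value when in doubt. Bleeding is a yes/no observation and less exposed, but it sits on the same listed item. Looking up a baseline pocket depth for the 2 mm rule may therefore put baseline MGI and bleeding in view as well. The single-use plaque comparison, a secondary endpoint, has a similar weakness: the pre- and post-brushing scores are one listed item, and the second examiners do both scorings.

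If anchoring occurs, true improvement is under-recorded in both arms and the estimated benefit of the power brush is understated. Scores cannot be retaken later.

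On allocation, someone who knows or can predict an assignment can influence a borderline eligibility decision, and the analysis cannot undo that. Some criteria leave room for judgement, such as "Other medical or dental conditions that would affect the study".

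**Working it through.** **1. What would an examiner be able to see?**
- Section 8 permits access; the patient schedule brings the record to the station; the contents list and Section 10 place earlier sheets in that record.
- The brush is handed over out of the examiners' sight and later brought in a brown bag (Section 4.5, Visit 2). These steps protect masking to brush. They do not separate an examiner from earlier scores.
- No text tells examiners to score without earlier sheets.

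**2. How many earlier MGI scores would exist by week 12?**
- Section 5.1 requires at least 20 scoreable teeth; Section 4.2.2 scores six sites on each.
- Per visit: 20 × 6 = 120, if all six sites are gradable.
- Baseline, week 2 and week 4: 3 × 120 = 360. This is a minimum. With 28 teeth (an assumption) it is 28 × 6 × 3 = 504.

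**3. The plan's own figures.** Section 7.1 gives alpha 0.05, power 0.95, 44 evaluable subjects, 40% dropout and 72 enrolled.
- 44 / (1 − 0.40) = 73.3, so 74 against the stated 72; in reverse, 72 × 0.60 = 43.2. The enrolment figure is reproduced to within two subjects.
- The 44 cannot be reproduced, because no effect size or standard deviation is given.

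**4. What would anchoring do?** This is an assumed model; the documents give no value for w.
- Recorded week-12 score = (1 − w) × true score + w × baseline.
- Recorded change = (1 − w) × true change in each arm, so the between-arm difference also shrinks by the fraction w.

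To illustrate power, assume a two-sided two-sample t-test at 0.05 with 22 per arm. Power 0.95 then implies a standardized difference of 1.11. (The planned analysis is a repeated-measures ANOVA, so this is illustrative only.) With s the share of change variance that does not shrink, the standardized difference becomes 1.11 × (1 − w) / √[(1 − s)(1 − w)² + s].

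| w | Loss of difference | Power, all spread shrinks (s = 0) | Power, half the variance unshrunk (s = 0.5) | Power, no spread shrinks (s = 1) |
|---|---|---|---|---|
| 0.1 | 10% | 0.95 | 0.93 | 0.90 |
| 0.2 | 20% | 0.95 | 0.89 | 0.82 |
| 0.3 | 30% | 0.95 | 0.83 | 0.71 |

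The standardized differences in the last column are 1.00, 0.89 and 0.78. The anchoring model itself gives s = 0. The last column requires all of the spread to be error added after anchoring, so it is an extreme bound.

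**5. Allocation: the order of events.**
- Eligibility is met before entry to the baseline procedure, and randomization follows screening.
- Baseline scores are recorded before the brush is assigned.
- Table 2 nevertheless marks a second eligibility check at baseline and lets the coordinator, a key holder, perform it. The patient schedule also lists the coordinator role for baseline check-in and for assigning the brush.
- An assignment made between screening and baseline could therefore be known at that check. No figure for selection bias can be derived.

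**The case against.** **On scoring.** The contents list describes the whole record; it does not say that completed earlier sheets stay in the packet carried at each visit. Section 10 has booklets reviewed after each visit and locked away. Section 8 may mean only that examiners need access because they write on source forms. All of this is fair: the documents do not show that any examiner consults an earlier sheet. What stands is that Section 8 grants the access in terms, one booklet with all forms is the natural reading of Section 10, and no rule excludes looking back.

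A reader might infer that the trial is biased toward the power brush, or that the record reveals the allocation. The documents support neither: examiners are masked to brush, and the assigned brush is not among the listed items as entries that examiners would see. A reader might also infer a sure loss of power; that depends on an unshrunk spread that the model does not produce.

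**On allocation.** The other side is strong here. Eligibility precedes baseline, clinical eligibility scores come from blinded examiners without the key, screening uses periodontal faculty, and medical and dental history is marked at screening only. Table 2 allows other staff to do the check. The opening part of Schematic 1 is missing from the copy reviewed, so the visit order may be clearer there. It would be wrong to conclude that enrolment is decided with the assignment known. What stands is only that a key holder is permitted to do the baseline check.

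**Conclusion.** The main point holds as a cheap improvement. Section 8 grants blinded examiners access that the scoring does not need, and the 2 mm rule gives them a reason to use it. The plausible harm is attenuation of change scores and of the between-arm difference, chiefly in MGI. Its size is not estimable from the documents. Under the assumed model the difference shrinks by w, while power lies between 0.95 and the extreme values of 0.90, 0.82 and 0.71 for w = 0.1, 0.2 and 0.3. At least 360 earlier MGI scores per subject would exist by week 12 if all sites on 20 teeth are gradable.

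The allocation point is secondary and minor. The order of events already removes most of the risk; what remains is an overlap of roles at one check. Neither point shows that the trial's results would be invalid.

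**What to change.** **Scoring**
- Reword Section 8 so that, until the study ends, examiners receive only the current visit's blank forms. Earlier sheets stay with the coordinator.
- Record the post-brushing plaque score on its own sheet. This removes the written prompt, though not memory if the same examiner scores both.
- Have existing non-scoring staff compare pocket depths with baseline after scoring and before the subject leaves, referring any 2 mm increase to the principal investigator. The safety rule is kept intact.

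**Allocation**
- Let an existing unblinded staff member who does no eligibility work hold the allocation list and release each assignment only after eligibility is signed off and baseline scores are recorded.
- Use the same wording in Section 4.5, Table 2 and the patient schedule.

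**Cost.** Protocol wording and minor form handling: one extra plaque sheet at baseline, a short check at each follow-up visit, and one staff member kept out of eligibility work. No change to sample size, visits or analysis.

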1. SELECTION AND WITHDRAWAL OF SUBJECTS

5.1. Admission Criteria

A subject who meets all the following criteria will be eligible to enroll in this study.

1. Age range 18 – 65 years
2. Routine manual toothbrush user
3. A Subject who agrees to use the assigned toothbrush as the only cleaning device for the study duration, refraining from daily interdental cleaning and/ or antiseptic mouthrinsing.
4. Mild to moderate gingivitis as measured by
 - A. Modified Gingival Index (MGI) average score of at least 1.2, and / or
 - B. Bleeding on Probing (BOP) of at least 20% of all sites but not more than 50% of sites.

CONFIDENTIAL

5. Probing Pocket Depth (PPD) of 4 mm or lower
6. At least 20 natural teeth – scoreable (crowns or bridgework are non-scoreable).

5.2. Exclusion Criteria

Any subject meeting one of the following criteria will not be included in the study.

1. Daily user of interdental cleaning devices, such as floss, floss picks, toothpicks, interdental brush, water flossing device
2. Regular user of antimicrobial mouthrinses within one week of entry into study
3. Professional prophylaxis within one month of entry into the study
4. Use of antibiotics within one month prior to the baseline exam
5. Signs of moderate to severe periodontitis or caries, categorized as PPD of 5 mm or higher and attachment loss of 3 mm or higher
6. Subjects with orthodontic bands and/or dental appliances.
7. Participated in an oral care related study in the last 90 days prior to this study
8. Pregnant or lactating women
9. Patients with a history of significant cardiovascular disease, diabetes, cancer, AIDS, or other organ impairment that would preclude their participation in the study
10. Acute/concurrent illness such as hepatitis, herpes simplex infections, influenza, etc.
11. History of rheumatic fever, cardiovascular valvular disease, artificial joint replacement or kidney or liver disorders
12. Chronic use of NSAID's (≥ 325 mg/day)
13. Current Smoker (within the last 3 months)
14. Other medical or dental conditions that would affect the study
15. Inability to commit to all necessary study visits from baseline to 12 weeks

5.3. Discontinuation criteria

The oral safety exam at the follow-up visits will include a thorough examination of the gingiva to look for any signs of gingival trauma, irritation or abrasion, as well as a periodontal probing. Any subjects who show signs of gingival trauma that appears to be toothbrush related will be exited from the study and the findings reported as Adverse Events. In addition, subjects may be discontinued due to the following reasons.

1. Voluntary discontinuation: subjects are free to discontinue their participation in the study at any time.
2. Safety concerns: the principal investigator may terminate a subject's participation if gingival trauma occurs and appears to be toothbrush related
3. Significant non-compliance to protocol: the principal investigator may terminate a subject's participation if subjects are shown to be non-compliant to the protocol
4. Incorrect enrollment: subjects who did not meet admission/exclusion criteria
5. Subject received any type of dental treatment/care other than those required in the study, for example use of interdental devices, mouthrinses, chewing gum or prophylaxis treatment, without consent of the investigator

Subjects who discontinue should be asked to a follow-up visit to observe any Adverse Events.

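### Sections 4.5 and 5.3 make exit for toothbrush-related gingival trauma both mandatory and optional, and no blinded person is named to judge relatedness

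*Combined protocol and SAP*

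**What the plan says.** On the exit rule:

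- **Section 5.3, opening paragraph.** Subjects with gingival trauma that seems to come from the brush "will be exited from the study and the findings reported as Adverse Events".
- **Section 5.3, line introducing the list.** "In addition, subjects may be discontinued due to the following reasons".
- **Section 5.3, item 2.** Under safety concerns, the principal investigator *may* end a subject's participation "if gingival trauma occurs and appears to be toothbrush related".
- **Section 4.5, Visit 3 (two weeks).** "Any subjects who show signs of gingival trauma that appears to be toothbrush related will be exited from the study".
- **Section 4.5, Visit 4 (four weeks).** "The PI will determine if any subject meets the discontinuation criteria as well as appropriate therapy to treat".

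On who knows the arm and who judges the event:

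- **Section 4.5, study procedure.** "only the PI and the Study coordinator will have access to the randomization key". PI also abbreviates Plaque Index in this protocol, but here it can only mean the principal investigator.
- **Patient Schedule, baseline.** The step of assigning the brush is listed under the principal investigator and study coordinator.
- **Table 2 and the Visit 1 text in Section 4.5.** The oral safety examination is done by blinded examiners 1 and 2. Section 4.2.1 has abnormal findings reported with an explanation.
- **Section 6.4.** The opinion on whether the device caused an adverse change is the investigator's. The section does not say that this person is blinded.

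**The concern.** The exit rule does two jobs. It decides who goes on using a brush that appears to have injured them, and it decides who is still in follow-up to supply later data. Tissue damage is a secondary objective (Section 3.2), abrasion-site counts are to be compared (Section 7.4), and the primary endpoint is change from baseline at 12 weeks (Section 4.3).

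If the same finding may lead either to exit or to continuation, two subjects with identical trauma can be treated differently and both decisions comply with the protocol. If the person deciding can also know the assignment, the difference may follow the arm. Section 7 does not say how subjects who exit are to be handled in the analysis. Section 7.1 counts only those left once drop-outs are removed.

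**Working it through.** The plan gives no figure on this point: no expected trauma rate, no expected number of exits, and no link between trauma and gingivitis response. The check is therefore a comparison of the texts.

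**Step 1. Is the trigger the same?** The opening paragraph of 5.3, the Visit 3 text and item 2 all require gingival trauma that appears related to the toothbrush. Item 2 sets no severity threshold, no visit restriction and no other condition that would make it a separate category.

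**Step 2. Is the consequence the same?** It is not.

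| Place | Outcome allowed once trauma is judged toothbrush related |
|---|---|
| 5.3, opening paragraph | exit |
| 4.5, Visit 3 | exit |
| 5.3, item 2 | exit or continue |
| 4.5, Visit 4 | principal investigator determines whether the criteria are met |

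Nothing in the documents says which sentence prevails. The list in 5.3 is introduced as additional to the mandatory rule, yet item 2 restates that rule's trigger with an optional outcome.

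**Step 3. Where does judgement enter?** There are two points:

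1. *Attribution*: does the trauma appear to come from the brush? This is needed under both wordings.
2. *Action*: given that it does, does the subject leave? This is open only under item 2.

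Replacing *may* with *will*, or the reverse, settles the second point only. At the first, blinded examiners record that trauma is present, but no section gives them the attribution. Section 6.4 gives the opinion on relationship to the investigator, and Visit 4 gives the determination to the principal investigator. Section 4.5 gives that person access to the key, and the Patient Schedule gives a part in assigning brushes.

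**Step 4. In which direction can the conflict act?** Against the mandatory sentence, item 2 can only keep traumatised subjects in the study; it cannot remove more of them. The risk from the conflict is thus that such subjects are retained more often in one arm than in the other.

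**Step 5. Which data depend on it?** The finding at the visit where trauma is first seen is recorded by the blinded examiner whether or not the subject leaves. What depends on the exit decision is what follows:

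- trauma at two weeks: the 4-week and 12-week abrasion counts and efficacy scores;
- trauma at four weeks: the 12-week abrasion counts and efficacy scores;
- trauma first seen at 12 weeks: little or nothing, since that is the last visit.

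**The case against.** The strongest reply is that much of the protection is already there. Blinded examiners do the safety examination, abnormal findings are written down with an explanation, and toothbrush-related trauma is to be reported as an adverse event. That stands. It limits the exposure to attribution, exit and later-visit data, and it means that detection of trauma is not in question.

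Item 2 might also be defended as merely naming who carries out the mandatory exit. Its verb is permissive, as is the line that introduces the list, so the text does not support that reading.

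Three stronger readings are tempting, and the documents do not support them:

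- **A reader might infer that item 2 lets the principal investigator remove poor responders and so raise the type I error by a calculable amount.** Item 2 applies only to subjects with trauma, and the mandatory sentence would remove those subjects anyway. Any such calculation would also have to assume how closely trauma and poor response coincide, and the documents say nothing about that.
- **A reader might infer that the comparisons are biased.** The text supports only that they could be.
- **A reader might infer that the principal investigator knows the arm at every decision.** The protocol establishes access to the key. Knowledge of the arm is a reasonable inference from the brush-assignment step, but it is not stated.

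**Conclusion.** The point holds as an internal contradiction in a safety rule, together with a gap in blinding. One event carries both a mandatory and an optional exit. The judgement that the event is toothbrush related has no stated blinded owner, and the discontinuation decision rests with someone who has access to the randomisation key. Because attribution is needed under both wordings, settling the wording would not by itself close the blinding gap.

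Identical events could be handled differently and exits could differ by arm, which could bias later-visit abrasion counts and the 12-week efficacy comparison. No size can be put on this: it would need the trauma rate in each arm and the relation between trauma and response, and the documents give neither. The case for correcting it rests on subject protection, the clear conflict of wording and the low cost.

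**What to change.** 1. Reconcile the sentences in Section 5.3 (opening paragraph and item 2) and Section 4.5 (Visits 3 and 4) to one rule, applied identically in both arms and at every follow-up visit. Which rule is a clinical decision, and this review does not propose one.
2. Under either rule, have the blinded examiner who already performs the safety examination record whether any trauma found appears to be caused by the toothbrush, before the principal investigator acts on it.
3. Report trauma findings and exits for trauma by arm.

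The cost is a wording change, processed as an amendment under Section 12, and one extra field on the examination form. No additional staff or visits are needed.
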